7.3 STUDY SCHEDULE

7.3.1 SCREENING

A signed and dated informed consent form will be obtained before any study-specific screening procedures are performed. Results of evaluations obtained as part of routine medical care, which are performed prior to obtaining

informed consent, may be used in place of the protocol-specified evaluations. Patients will acknowledge and agree to the use of this information for the study by giving informed consent.

At the Baseline Visit, patients will be assigned by the IWRS a unique permanent identification number (referred to as the patient identification number) such that all randomized patients from each center are given consecutive identification numbers by the IWRS in successive order of inclusion. We will utilize the REDCap randomization module.

Prospective study patients will have presented to the hospital for urgent therapy for AHF. Potential patients will be identified either en route to or upon arriving at the ED/hospital. Routine assessments associated with usual patient care may be used for the purposes of screening and may be completed in any order. Study specific procedures must be completed only after Informed Consent is obtained.

Randomization will occur during the patients ED stay. This may occur at any time during their ED stay.

The following procedures will be performed prior to or during Screening:

- Obtain written informed consent (must be performed as the first study-specific procedure)
- Review and record medical history
- Record prior and concomitant medications
- Physical examination (including height and weight when reasonably possible)
- Vital signs measurements (includes systolic and diastolic blood pressures, heart rate, body temperature, oxygen saturation reading and respiratory rate)
- 12-Lead Electrocardiogram per standard practice
- Blood collection for local laboratory tests, including BNP or NT-proBNP, and pregnancy test if applicable per local standard practice.
- Inquiry about Adverse events

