7.3.7 SCHEDULE OF EVENTS TABLE

Schedule of Events Timepoint/Visit	Screen	Baseline	ARM 1 - PreDischarge from SSU	ARM 2 - PreDischarge from Hospital Floor	30-Day & 90 Day Follow up
Informed Consent	X				
Medical History		X			
Physical Exam		X	X	X	
Clinical lab tests*		X	X~	X~	
ECG*		X			
CXR*		X			
KCCQ (QoL) & SF-12			X	X	X
Oberst Caregiving Burden Scale and Bakas Caregiving Outcomes Scale			X	X	X ¹
HF Guideline Assessment			X	X	
Collect concomitant meds		X	X	X	
mRUQ-HF (resource utilization)					X ²
Cost Effectiveness Measures (i.e. DRG)					X
Guideline adherence assessment		X	X	X	X ¹
SCPC Discharge Criteria Adherence			X	X	
Assessment of AE/SAE's through 5 days			X	X	
Vital Status, ED visits, Hospital days, Re-admission status			X	X	X
Subject Payment			X	X	X ²

*per standard of care. Typical labs include: Na, K, renal function, HgB, troponin, Natriuretic Peptide levels. ~only if performed per usual care

SOC = standard of care, ED = Emergency Department, QoL = quality of life, HF = heart failure, mRUQ = modified resource utilization questionnaire, EMR = electronic medical record, DRG = diagnosis related group

¹Only through 30 days

²Sites may choose to make a single payment or to divide into 2 payments.

³only at 90 days

NOTE: If patients are hospitalized from the SSU, ONLY the following assessments should be collected. Otherwise, the pre-discharge assessments will apply.

- Physical exam
- Clinical lab tests
- Con meds
- SCPC discharge criteria. This would be conducted twice. Once in SCPS prior to hospitalization and again at discharge.

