10.1.1 ENDPOINTS AND RATIONALE

To ensure patient-centered endpoints, we twice met with patients and caregivers through two community engagement studios.⁵⁴ Patients prefer to be healthy and have a good QoL. If a safe alternative is available, patients prefer not to be hospitalized.

The **primary outcome** is **days alive and out of hospital (DAOOH) at 30 days post-randomization**. Unlike time-to-event analyses that ignores repeat events and gives equal weight to components of a composite endpoint,⁵⁵ DAOOH accounts for both frequency and duration of hospitalization and also weights mortality most heavily.^{55,56} This endpoint has also been suggested as a quality metric rather than re-hospitalization alone.⁵⁷

The **two secondary outcomes** are 1) **QoL using the KCCQ**. Patients desire not only to live longer, but to live better; or at minimum, not be worse after an acute health care related event.⁵⁸ Patients with advanced HF would trade survival time (or days alive) for a better QoL.⁵⁸ Our pilot work supports the feasibility of assessing QoL in the acute setting and suggests changes in scores are related to hospital re-visits.⁵⁹ We hypothesize that fewer days in the hospital in our SSU arm will also lead to a greater QoL. Interviews of hospitalized AHF patients suggest **they would prefer a shorter hospital stay or avoid an admission altogether**, assuming safety and outcomes are similar or better than hospitalization. Thus, assessing QoL is a key aim.

The KCCQ is a patient-reported, validated survey instrument designed to measure QoL in chronic HF patients.⁶⁰ Lower scores equal lower patient-reported QoL. **KCCQ scores predict adverse outcomes – namely hospitalization and mortality.** Importantly, the KCCQ demonstrates responsiveness to clinical change.⁶⁰⁻⁶²

A change of five points has been previously shown to be clinically significant, and will be assessed prior to discharge and day 30 post-randomization.⁶²

2) Cost effectiveness analysis, described in detail below.

NOTE: For patients randomized to SSU who worsen PRIOR to going to SSU, this will be counted the same as a hospitalization from the SSU.

ADDITIONAL ENDPOINTS

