10.4.3 ANALYSIS OF THE SECONDARY ENDPOINT(S)

QoL: An AHF SSU strategy of care will lead to significant improvement in QoL scores at 30 days post-discharge compared with usual care. QoL will be assessed with the KCCQ.⁵⁹

Sample Size Calculation: The standard deviation of 1-week KCCQ change after acute heart failure is 20.8.⁷³ Below are the numbers of subjects (both arms combined) required to detect various intervention effects with 80% power and type I error controlled at 0.05 (two-sided) in the table.

Similarly, the number of subjects (both arms combined) required to detect various effect size for caregiver burden (CB) with 80% power and type I error controlled at 0.05 (two-sided) is listed below. The effect size is defined as the difference in CB score divided by the standard deviation. It is a widely-used measure of treatment effect, which is used here because the standard deviation of CB in the target population if it has not been robustly studied. Because we changed CB scales, we will use established MCID for each established scale.

KCCQ: Sample size (both arms combined)	% of data attrition	Difference in KCCQ change
480	10%	5.3
360	33%	6.2
240	55%	7.6
120	78%	10.7

KCCQ QoL Analysis: The KCCQ will be compared between the two arms using the same method as in Aim 1. We will consider three ways of analysis with different outcomes based on KCCQ scores. First, we will exclude subjects who die without KCCQ in the analysis. Second, we will set KCCQ=0 for those who die without the 30-day KCCQ and include these people in the analysis. Third, we will create a composite binary endpoint of KCCQ<c or death, where c is a threshold. Chi-square test and logistic regression will be used to compare this outcome. We will select several relevant values for the threshold c and tabulate the results. The three analysis schemes allow us to understand how robust the comparison of KCCQ is with respect to different treatments of death.

Cost-Effectiveness Analysis:

To assess the effectiveness of short stay unit (SSU) management, we will analyze the patient outcomes as defined by cost, quality-of-life (QOL), medical utilization, and caregiver burden using regression analysis, and combine these results into a multifaceted incremental cost-effectiveness ratio (ICER).

$$ICER = \frac{C_{SSU} - C_H}{E_{SSU} - E_H}$$

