Here, E_{SSU} and C_{SSU} are the effectiveness and cost, respectively, of the SSU, while the E_H and C_H are the effectiveness and cost of the hospital admission. The incremental cost effectiveness ratio allows us to estimate the additional cost associated with SSU treatment proportionate to the increased effectiveness of its patient outcome. We expect SSU treatment to dominate hospital admission, resulting in greater effectiveness at a lower cost.^{1,2} Therefore, we expect ICER to be negative, reflecting the cost savings of implementing SSU treatment.

Our goal is to evaluate the cost-effectiveness of the SSU strategy from a societal perspective, as we will account for the costs of care from both the hospital/insurer perspective and patient point-of-view. As discussed in more detail below, our primary challenges lie in obtaining accurate and complete costs incurred by the patient outside of the hospital setting. Given this potential limitation, at minimum, our CEA evaluation will be from the hospital/payer perspective.

We will use an episodic approach to costing, which accounts for any cost shifting to a later point in time. This is the preferred approach for the Centers for Medicaid and Medicare services. Specifically, we will examine the total cost of patient care from the index ED visit (study enrollment) for a period of 30 days. In the context of the episode, we will analyze the incidence of readmission, total days of hospitalization, utilization of outpatient care, total cost, and caregiver burden.

The outcome variables of interest are cost, effectiveness, and other characteristics of participant experience. Costs will be defined by total billable hospital costs (Table 1) and patient costs. Hospital costs include payments by insurance, patients, and third parties. While this type of cost information is most accurate for our purposes, it is also the most difficult to obtain. Recognizing the phenomenon of 'upcharging,' we will obtain hospital charges from each site as this is the easier data to acquire.

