Given the difficulty of obtaining costs and payments, we will standardize hospitalization and SSU costs using Medicare reimbursement rates (See Sensitivity Analysis Section below). Patient costs will include self-reported out-of-pocket costs and time costs using a modified version of a previously published survey. (see attached) One limitation of self-reported data will be potential mismeasurement due to recall bias. Should the patient-completed survey lack a sufficient response rate for outpatient analysis, we will limit our analysis to the hospital portion of the treatment. Effectiveness will be defined by SF-12 and SF-6D metrics of patient self-reported QOL. The SF-12 has been previously used to evaluate outcomes for HF patients.³ Effectiveness in ICER computations is often measured using quality-adjusted life years (QALYs), defined as:

$$QALY = \sum_{t=t_0}^Z \delta^{t-t_0} q_t P_t$$

where P_t is the probability of surviving to each year t , q_t is the preference weight, and δ is the time-discounting factor. As the SF-12 does not allow direct assessment of QALYs, we will convert the score into a SF-6D preference based score using the six health dimension scores from the SF-12^{4,5} to generate the preference weights and probabilities necessary to conduct the cost-utility analysis. Since the participant will be completing the SF-12 survey at the beginning and end of the episode, all models estimating the effectiveness will include the baseline score in the vector of participant characteristics. Aside from cost and effectiveness, we will analyze the incidence of re-admission, the utilization of outpatient care, and caregiver burden, as detailed in our statistical analysis plan. While the incidence of re-admission will be obtained from both the electronic health record and patient self-report, the outpatient and caregiver burden are self-reported.

For each outcome variable of interest (patient costs, hospital costs, total episode costs, SF-12 scores, SF-6D scores, QALYs, incidence of readmission, total days of hospitalization, utilization of outpatient care, nursing care, and caregiver burden) we will estimate a predictive model accounting for the heterogeneity among participants in the intervention and control groups.

$$Y_i = \alpha + \beta_1 SSU_i + \beta_2 D_i + \beta_3 R_i + \beta_4 D_i * R_i + \beta_5 D_i * SSU_i + \beta_6 R_i * SSU_i + \beta_7 D_i * R_i * SSU_i + \gamma X_i + \delta H_h + \kappa_h + \tau_t + \varepsilon_i$$

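### No KCCQ or SF-12 is scheduled before randomization, so a change score or a 'baseline' adjustment would rest on a score taken after arm-dependent treatment

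*Combined protocol and SAP*

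**What the plan says.** - **Randomization.** Section 7.3.1: "Randomization will occur during the patients ED stay". The screening procedures listed there include no questionnaire.
- **Questionnaire times.** The schedule in 7.3.7 marks KCCQ and SF-12 at pre-discharge (from the SSU in Arm 1, from the hospital floor in Arm 2) and at the 30- and 90-day follow-up. The Screen and Baseline columns are empty. Section 10.1.1 agrees for the KCCQ: "A change of five points has been previously shown to be clinically significant, and will be assessed prior to discharge and day 30 post-randomization".
- **KCCQ variable.** The power table in 10.4.3 is headed "Difference in KCCQ change" and uses an SD of 1-week change. The analysis text below it reads as if the day-30 score were tested: "we will set KCCQ=0 for those who die without the 30-day KCCQ", plus a binary endpoint of score below a threshold or death.
- **SF-12.** The cost-effectiveness text in 10.4.3 says "Since the participant will be completing the SF-12 survey at the beginning and end of the episode", and that "all models estimating the effectiveness will include the baseline score in the vector of participant characteristics". The episode runs "from the index ED visit (study enrollment) for a period of 30 days".
- **Patients admitted from the SSU.** Under the 7.3.7 table: "NOTE: If patients are hospitalized from the SSU, ONLY the following assessments should be collected". The list that follows has physical exam, labs, concomitant medications and SCPC discharge criteria, but neither questionnaire. Section 10.5 assumes that 40% of the SSU arm is admitted.
- **Day 30.** It is counted from randomization in 10.1.1, but from discharge in 7.3.3, in Hypothesis 1b (10.2) and in 10.4.3.

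**The concern.** Quality of life is the first secondary endpoint and half of the goal stated in section 3. Randomization protects a comparison of day-30 scores. It does not protect a comparison that subtracts or conditions on a score which the assigned setting, or the time spent in it, may already have moved. Section 10.1.1 itself describes the KCCQ as responsive to clinical change, so such movement is possible.

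If one arm looks better or worse at discharge, that gap passes with reversed sign into a change analysis in full, and into an adjusted analysis in part. A change analysis could also lose patients from one arm only, namely those for whom SSU care was not enough. In an unblinded trial, leaving the tested variable open is a weakness in itself.

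**Working it through.** **1. Order of events.** Randomization is in the ED; the first scheduled score is just before discharge. Section 6.1.1 gives the stay as under 24 hours in the SSU and a median of 4.3 days for inpatients. The risk-matched comparison in 2.2 gives medians of 25.7 and 58.5 hours, a gap of 58.5 − 25.7 = 32.8 hours. The first score is therefore post-randomization, at an arm-dependent time.

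**2. The plan's own KCCQ figures.** Inputs from 10.4.3: SD of change 20.8, 80% power, two-sided 0.05, equal arms. With 240 per arm:
- SE = 20.8 × √(2/240) = 1.90.
- Detectable difference = (1.960 + 0.842) × 1.90 = 5.32 (5.33 with the t distribution), against 5.3 in the plan.
- The other rows give 6.16, 7.55 and 10.73 (t), against 6.2, 7.6 and 10.7.
- 480/0.9 = 533.3, so 534 randomized.

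The table is right on its own inputs, for change.

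**3. Form of the bias.** Let g be the arm difference (SSU minus usual care) in the pre-discharge score.
- Change score: expected estimate = true day-30 effect − g.
- Adjustment with slope b: expected estimate = true day-30 effect − b × g.
- Day-30 score alone: expected estimate = true day-30 effect.

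**4. Illustrative size.** The documents give no value for g, so 1, 3 and 5 points are assumptions. For adjustment, assume a correlation and slope of 0.5. An SD of change of 20.8 then implies a score SD of 20.8/√(2 × 0.5) = 20.8 and a residual SD of 20.8 × √(1 − 0.25) = 18.0. Two-sided rejection rates with no true day-30 difference, 240 per arm:

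| Gap (absolute) | Change | Adjusted, b = 0.5 | Day-30 score |
|---|---|---|---|
| 1 | 8.2% | 6.1% | 5% |
| 3 | 35.1% | 14.9% | 5% |
| 5 | 74.8% | 32.9% | 5% |

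A simulation of 5,000 trials per gap gave 8.5%, 34.3% and 74.5% for change; 6.2%, 14.0% and 31.3% for adjustment; and 5.0%, 4.3% and 5.0% for the day-30 score. At a gap of 5, slopes from 0.3 to 0.7 give 17% to 51% for adjustment. These rates are on the KCCQ scale. For SF-12 only the algebra in step 3 carries over, because no SF-12 SD is given.

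**5. One-sided loss of first scores.** If the 40% admitted from the SSU have no first score, 240 × 0.6 = 144 SSU patients remain against 240. Then SE = 20.8 × √(1/144 + 1/240) = 2.19, and the detectable difference is 2.802 × 2.19 = 6.14 (6.16 with t), up from 5.3, before any selection bias.

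**6. Power if the day-30 score is tested.** Its SD is not in the documents. Holding the SD of change at 20.8 and assuming correlation r, the score SD is 20.8/√(2(1 − r)):

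| r | Score SD | Detectable, unadjusted | Detectable, adjusted for a true baseline |
|---|---|---|---|
| 0.3 | 17.6 | 4.5 | 4.3 |
| 0.5 | 20.8 | 5.3 | 4.6 |
| 0.7 | 26.9 | 6.9 | 4.9 |

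The stated 5.3 points is therefore unverified for the day-30 score, not shown to be wrong.

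**The case against.** The strongest reply is that the plan does not commit itself to testing change. The analysis text in 10.4.3 handles death with rules that fit a day-30 score, and Hypothesis 1b speaks of scores at 30 days. On that reading the KCCQ bias does not arise. This is fair. What remains is that the variable is never named and the power table is built on another one.

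Second, the gaps are assumed. The largest equals the change that the plan calls clinically significant, and a real difference in post-discharge change is a legitimate quantity, only not the day-30 effect. This also stands: the rates show sensitivity and are not evidence about this trial.

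Third, under 24 hours against 4.3 days probably overstates the contrast, since the trial enrols lower-risk patients and expects many SSU patients to be admitted. True, but a smaller contrast does not make the first score pre-randomization.

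Fourth, the note under 7.3.7 can be read as a short set at transfer to the ward, followed by the ordinary pre-discharge assessments, so that no one is lost; section 10.4.5 also plans multiple imputation. That is plausible. Even so, the first score of those patients would come at a later hospital discharge, and the note does not settle which reading applies.

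Finally, the SF-12 text is sound if the first survey is given in the ED before randomization. The text does not say that it precedes randomization, and the schedule has no slot for it.

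**Conclusion.** The concern holds as a conditional design point. Followed as written, the schedule yields no pre-randomization KCCQ or SF-12. The SF-12 adjustment would then use a post-randomization value, and so would KCCQ if change is tested. Neither the direction nor the size of the bias can be found from the documents; the rates above rest on assumed gaps and, for adjustment, an assumed slope. The loss to 144 against 240 rests on one reading of an ambiguous note. The day-30 score compared by randomized arm has neither problem. The KCCQ power table contains no arithmetic error. The inconsistent anchor for day 30 is a related point: counted from discharge, the measurement date itself depends on length of stay, which the intervention is meant to change.

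**What to change.** 1. In 10.4.3, name the day-30 KCCQ score, and the day-30 SF-6D utility for the cost-effectiveness analysis, as the outcomes. Anchor them at day 30 after randomization in both arms, and bring 7.3.3, 10.2 and 10.4.3 into line with 10.1.1.
2. Compare arms using site and pre-randomization covariates only. Do not subtract or adjust for the pre-discharge score; it can be reported descriptively.
3. Preferably, give the existing KCCQ and SF-12 once after consent and before randomization, use them as the baseline covariates, and add them to the Baseline column of 7.3.7 so that it agrees with the cost-effectiveness text. Section 10.1.1 reports pilot work supporting QoL assessment in the acute setting.
4. State under 7.3.7 that patients admitted from the SSU still receive the day-30 questionnaires and are analysed in the SSU arm.
5. State the SD of the analysed quantity in the power table.

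The cost is SAP wording plus one existing questionnaire set, a few minutes of patient time in the ED. If that is not feasible, items 1, 2, 4 and 5 still remove the bias, with some loss of precision.

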Decreasing hospital stays may increase caregiver burden. Thus, we will also assess caregiver burden, using both the Oberst Caregiver Burden and Bakas Caregiver Outcome Scales, both validated instruments prior to discharge and again at 30 days.⁶⁸ Other measures of caregiver burden in HF have either not involved input from actual caregivers or missed important conceptual domains.⁶⁸ Effective caregivers has been associated with improved quality of life, lower hospitalization rates, and reduced mortality.^{68,69} As our primary focus is on the patient, the eligibility criteria for the caregiver will be broad, essentially including any person who after separate written informed consent, acknowledges themselves as the primary caregiver for the patient.

Out-of-pocket costs directly impact patients. As such, we will assess healthcare utilization from a societal perspective using the Modified Resource Utilization Questionnaire for Heart Failure (mRUQ-HF).⁷⁰ The mRUQ-HF is a 14-item self-report questionnaire of comprehensive lists of choice related to healthcare utilization. (See Appendix trial protocol) Exploratory analysis will occur in two steps: 1) Determination of resources consumed or related; 2) Assignment of 'value' to the resources consumed.⁷¹ This two-step process allows for transparency of assigned costs. Hospital costs will be assigned per individual hospital cost-accounting. Where monetary values are not directly self-reported, Medicare fee schedules will be used for uniformity.

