Intervention Monitoring: To ensure fidelity of each component of the intervention between study arms, we will also measure the following individual components of the intervention throughout the trial at both the site and overall study level: 1) Baseline patient characteristics, 2) Medicine reconciliation 3) Guideline-HF adherence 4) SSU AHF protocol adherence, 5) admission rates from the SSU 6) Quality of Life/Caregiver Burden Questionnaire response and completeness, 7) Hospitalized patients discharged within 48 hours, and 8) Follow up completed at 30 days. These analyses will be reported every 3 months to the Steering Committee to allow for course correction as needed. In addition, these will be reported at the conclusion of the study as well as at quarterly enrollment milestones to the DSMB.

Sensitivity Analyses: Some baseline covariates such as co-morbidities, medications, renal function, serum sodium, potassium, b-type natriuretic peptide (BNP) or NT-pro BNP, and blood pressure, may not be well-balanced between the two arms despite randomization. These covariates are known markers of risk in AHF patients and are part of the standard assessment for the vast majority of AHF admissions. We will use the inverse probability weighting approach to adjust those covariates with poor balance between the arms as part of a sensitivity analysis.⁷⁵ We will then compare these results with those from the two-sample t test. In addition, if the DAOOH, QoL, caregiver burden, or mRUQ-HF endpoints are found to be non-normal in distribution, the Wilcoxon Rank-Sum test will be used for comparison as a sensitivity analysis.

Modified Resource Utilization Questionnaire for Heart Failure (mRUQ-HF).⁷⁰ The mRUQ-HF is a 14-item self-report questionnaire of comprehensive lists of choice related to healthcare utilization. (See Appendix trial protocol) Exploratory analysis will occur in two steps: 1) Determination of resources consumed or related; 2) Assignment of 'value' to the resources consumed.⁷¹ This two-step process allows for transparency of assigned costs. Hospital costs will be assigned per individual hospital cost-accounting. Where monetary values are not directly self-reported, Medicare fee schedules will be used for uniformity. This will be captured at 90 days and will include the hospitalization when patients answer the questionnaire.

All Cause Mortality and All-Cause Rehospitalization Endpoints:

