0 Did Not Change 1

2

3 Changed for the Best

OBERST CAREGIVING
BURDEN SCALE.docxBCOS120715 -
modified HF.doc**17.3 MRUQ-HF**

MODIFIED RESOURCE UTILIZATION QUESTIONNAIRE FOR HEART FAILURE
(SOCIETAL PERSPECTIVE)

This is a series of questions about your health care that you have received during **past 3 months**.

1. During the **past 3 months**, how many times have you had **appointments or visits** at any of the following clinics or providers?

Clinics / Providers	Number of Appointments/Visits	How Long (hours)	Reason for Appointments/Visits
Cardiologist			
Home health services			

Nurse clinic visit			
Emergency department			
Hospitalization			
Other healthcare appointments			
Endocrinologist			
Nephrologist			
Ophthalmologist			
Allergist/Ear Nose Throat clinic			
Alternative/ homeopathic medicine			
Chiropractor			
Dentist			
Dermatologist			
Family physician/ internal medicine/ primary care physician			
Gastroenterologist			
Mental health professional			
Orthopedist			
Physical therapist			
Physician assistant			
Podiatrist			
Other:	—		

2. Not including the visits just listed, during the **past 3 months**, how many times did you communicate (**telephone, e-mail, text, fax**) with anyone (physician, nurse, or technical support) regarding your heart condition?

	Reason for contact	Number of contacts for information needed or communication	Type of communication (phone, e-mail, etc)
Physician			
Nurse practitioner			
Nurse educator			
Social worker			
Technical (e.g., pacemaker company)			

Other:			
--------	--	--	--

3. Within the **past 3 months**, have you been visited in your home for **heart failure education**, attended a class, or a support/informational group? Yes No

3a. If **yes**, how long was each educational session and who participated in the education process with you.

	Purpose	Length of Session	How many times	Who participated with (spouse/child/sibling/other)
Visited at home				
Attended a class				
Heart failure support group				
Other:				

4. Within the **past 3 months**, have you or other family members attended **mental health counseling** sessions for support? Yes No

4a. If **yes**, how long was each counseling session and who participated in the process with you.

	Purpose	Length of Session	Who participated with (spouse/child/sibling/other)
Session 1			
Session 2			
Session 3			
Session 4			

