5. Approximately how much did you spend for **purchase or rental of health care-related equipment/medications** for your health care over the **past 3 months**?

Item related to heart failure	Where purchased (mail order, pharmacy, or clinics)	Cost that your insurance did not cover
Medication		
Scale for weighing self		
Oxygen		
Heart failure device		
Batteries for device		
Alcohol wipes		
Dressing tape		
Item related to other conditions	Where purchased (mail order, pharmacy, or clinics)	Cost that your insurance did not cover
Other medication		
Blood glucose meter		
Test strips		
Lancets		
Insulin (include all types)		
Insulin pen		
Insulin pump reservoirs and cartridges		
Insulin pump infusion sets		
Batteries for pump / meter		
Infusion set inserter		
Continuous glucose monitor		
Continuous glucose monitor sensor		
Ketosticks		
Supplies / food to treat hypoglycemia		
Pump accessories		
Medic alert bracelet or necklace		
Other supplies:		

Item related to mobility	Where purchased (mail order, pharmacy, or clinics)	Cost that your insurance did not cover
Wheelchair		
Scooter		
Walker		
Cane		
Hospital bed		
Ramp		
Shower chair		
commode		
Other:		

6. Do you receive your health insurance from an employer? Yes No

6a. What is your **annual** health insurance premium cost? \$_____

6b. What is your **annual** health insurance deductible? \$_____

The following questions ask about the effect of your health problems on your ability to work and perform regular activities during **past 3 months**. Please fill in the blanks or circle a number, as indicated.

7. During the past 3 months, how much time (minutes) **each week** did you spend taking your medications, following your diet (making choices and eating), and weighing yourself? _____ minutes

8. During the past 3 months, how much time was spent taking care of technical issues (such as caring for heart related equipment)? _____ minutes

9. Are you currently employed (working for pay)? Yes No Retired

► If you answered '**No**' or '**Retired**', skip Questions 10 ~ 13 and go to Question 14.

10. During the past 3 months, have you been absent from work because of illness?

Yes No

10a. If **yes**, how many days? _____, partial days: _____

11. During the past 3 months, how many hours did you actually work? _____ hours

12. Does your workplace employ a nurse? Yes No

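### The mRUQ-HF costing is called societal, but drugs, supplies and equipment enter only at the patient's uninsured share (minor; exploratory 90-day endpoint)

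*Combined protocol and SAP*

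**What the plan says.** Section 10.1.1 (Additional Endpoints) opens the topic from the patient's side, "Out-of-pocket costs directly impact patients", and then declares a societal perspective for the mRUQ-HF. Resources used are identified first and valued second. Two pricing rules follow: "Hospital costs will be assigned per individual hospital cost-accounting" and "Where monetary values are not directly self-reported, Medicare fee schedules will be used for uniformity". Section 10.4.3.1 repeats both and adds the timing: "This will be captured at 90 days and will include the hospitalization when patients answer the questionnaire". The endpoint is exploratory (4.2.3).

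The form is printed in 17.3. Item 1 lists clinics and providers, including "Home health services", and records "Number of Appointments/Visits", hours and reason, with no dollar column. Item 5 lists medication, oxygen, devices, consumables and mobility aids. Its columns are the place of purchase and "Cost that your insurance did not cover". It has no column for quantity or for full price. The only other dollar fields are the annual premium and deductible (items 6a and 6b).

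**The concern.** A societal cost counts what a resource costs whoever pays for it. The plan's rule gives priority to a self-reported dollar figure where one exists. For goods used at home, the only figure the form can return is what the patient paid after insurance. The rule therefore replaces the price of the resource with the patient's part of it, and no other rule adds the insurer's part back.

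Two things are at stake. The reported level of resource use would be too low under its stated label. It would also move with insurance status: a fully covered drug is worth zero and the same drug bought without insurance is worth its full price. Insurance status is one of the trial's pre-specified subgroup factors (10.4.3.1), so cost levels set side by side across those groups would partly reflect who pays, not what was used.

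**Working it through.** The plan gives no cost figure here, so there is nothing to reproduce. The check follows the pricing rule through the form and then illustrates its effect.

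**Step 1. The rule applied field by field (10.1.1 and 10.4.3.1 against 17.3).**

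| Resource | What the form records | Price under the rule |
|---|---|---|
| Hospital care | Count, hours (item 1) | The hospital's own accounting cost |
| Clinic, nurse and home health visits | Count, hours (item 1) | Medicare fee, as there is no dollar field |
| Contacts, education, counselling | Counts or session length (items 2 to 4) | Medicare fee, as there is no dollar field |
| Drugs, oxygen, devices, supplies, mobility aids | Uncovered dollars (item 5) | The uncovered dollars |
| Premium, deductible | Annual dollars (items 6a, 6b) | Use not stated |

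Three price bases are in play. The one for item 5 is the patient's share alone.

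**Step 2. Effect on the level.** Let F be the full price of item 5 goods and c the insurer's share. The documents do not give c, so it is an assumption.

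Recorded value = (1 − c) × F. With F = 100:

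- c = 0: 100
- c = 50%: 50
- c = 80%: 20
- c = 90%: 10
- c = 100%: 0

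This applies in both arms.

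**Step 3. Effect on the comparison.** Suppose SSU saves 100 in hospital cost and uses D more of item 5 goods at full price, with the same c in both arms. The figure of 100 and the values of D are assumptions.

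True difference = −100 + D. Recorded difference = −100 + (1 − c) × D. Error = −c × D.

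| D | True | Recorded at c = 50% / 80% / 90% | Saving overstated by |
|---|---|---|---|
| 0 | −100 | −100 / −100 / −100 | 0% / 0% / 0% |
| 10 | −90 | −95 / −98 / −99 | 6% / 9% / 10% |
| 25 | −75 | −87.5 / −95 / −97.5 | 17% / 27% / 30% |
| 50 | −50 | −75 / −90 / −95 | 50% / 80% / 90% |

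If use is equal but coverage differs, a gap appears from nothing. With 100 of goods in each arm and coverage of 90% against 80%, the recorded values are 10 and 20, a difference of 10 with no difference in resources.

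**Step 4. Does another section repair it?**

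- The sensitivity analysis in 10.4.3 that uses CMS reimbursement covers hospitalization and SSU costs only.
- 10.4.3 concedes that patient costs outside hospital may be incomplete and subject to recall error. That concerns missing or inaccurate answers. Here a complete and accurate answer still measures the wrong quantity.
- Multiple imputation under 10.4.5 would impute uncovered amounts, so it carries the same limitation.

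None of these restores the insurer's share.

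**The case against.** The strongest reply is that the gap is narrow and its effect on the comparison is not shown. Most of that stands.

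- **Care at home.** A reader might infer that all care moved from hospital to home is undercounted. It is not. Home health, nurse and clinic visits are counted in item 1 and take the Medicare fee. Only item 5 goods are affected.
- **Direction.** A reader might infer a bias towards SSU. That needs a difference between arms in use or coverage of item 5 goods over the form's three-month recall. Both arms go home, and the documents give no such difference. On assumed figures of $200 to $500 of goods spread evenly over 90 days, daily use is $2.22 to $5.56. With 75% to 100% unrecorded, one extra day at home leaves out $1.67 (0.75 × 2.22) to $5.56 per patient, and four days about $7 to $22. Section 2.2 cites a charge difference of about $3600, a rough yardstick only because it is in charges.
- **Blank boxes.** A reader might infer that an empty item 5 cost box is filled with a Medicare price while a completed box counts at the uncovered share. The fallback reads more naturally as covering items with no dollar field. An entirely blank row shows no resource to price. The case arises only if the place of purchase is given and the cost is missing. The wording should still close it off.
- **Cost-effectiveness analysis.** A reader might carry the problem into the 30-day analysis in 10.4.3. That section does not name its patient-cost survey, and it asks for out-of-pocket costs, which item 5 suits. The link is not established.
- **Full price.** Table 1 notes that CMS-based measures leave out the patient's share. A Medicare price may therefore be a payer share and not a full price. This changes the description of the mix but does not make it a societal cost.

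What the reply does not remove is the central point: the stated rule, followed exactly, omits the insurer's share of item 5 goods under a societal label.

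**Conclusion.** Wrong as written, and minor. The mRUQ-HF result combines accounting cost, Medicare fees and the patient's uninsured share, so it is not a societal cost, and it varies with insurance status for the same use. The understatement of levels in both arms follows from the documents for any good that insurance partly or fully covers. Its size depends on the insurer's share, which they do not give: half to nine-tenths of the value of these goods at assumed shares of 50% to 90%.

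The arm comparison is unaffected if use and coverage of these goods are the same in both arms. The overstated savings in the illustration (6% to 90%) hold only under its assumed differences and are not estimates for this trial. The documents do not support a claim that the analysis favours SSU. The endpoint is exploratory, and neither the primary endpoint nor Aim 2 depends on it.

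**What to change.** In 10.1.1 and 10.4.3.1, replace the pricing sentence with rules to this effect:

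1. Report the item 5 uncovered amounts as a separate patient out-of-pocket total. Do not add them to fee-schedule or hospital costs as if they were the full price of the resource.
2. Handle missing out-of-pocket amounts under 10.4.5. Never fill them with a Medicare price.
3. Value non-hospital services from one stated price list in both arms, and say whether that list includes the patient's share.
4. Call the combined figure societal only if item 5 goods are also priced from that list, as a sensitivity analysis with stated quantity assumptions. Otherwise describe the result as hospital/payer cost with out-of-pocket cost alongside.
5. State whether the premium and deductible (items 6a and 6b) enter any total.

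The cost is SAP wording and some pricing work, with no new patients or visits. The rules should be settled before cost data are seen by arm. The drawback is that repricing item 5 goods can only be approximate. The item records no quantities, and fully covered goods may be left blank. The pre-discharge medication record (7.3.7) neither measures use over 90 days nor covers equipment. If that is judged too weak, points 1 to 3 with the plainer label are enough.
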